The severity of insulin resistance depends on numerous factors, such as weight, age, heredity, oxidative stress, and endocrine history (4-8). As a net effect, glucose metabolism is modified, resulting in elevated fasting glucose levels or glucose intolerance and will manifest T2DM within 3 to 5 years (9). On the other hand, hyperbaric oxygen therapy (HBOT) is defined by the Undersea and Hyperbaric Medical Society (UHMS) as treatment where a patient intermittently breathes 100% oxygen at a pressure above sea level pressure (a pressure greater than 1 atmosphere absolute, ATA) (10, 11) and its benefits have been demonstrated in stroke, through the promotion of cerebral oxygenation, metabolic improvement, anti-inflammatory barrier, protection of cerebral blood flow, modulation of intracranial pressure, decrease of oxidative stress and apoptosis, increase of vascular and neural regeneration (12).

HBOT induces an increase of 100% of oxygen in blood and tissues during the procedure helping to maintain the integrity and function of tissues and cells (13), stimulates the antioxidant response in plasma and regulates the processes of angiogenesis, vascular tone by increasing the levels of vascular endothelial growth factor (VEGF) and decreasing the levels of endothelin-1 (ET-1). Different factors such as age, oxidative stress, diabetes and chronic inflammation (14, 15), play an important factor in the development of diabetic foot or diabetic neuropathy (16, 17).

It has been described that the hyperbaric chamber increases the levels of circulating free fatty acids, so that chronic inflammation could be associated with an increase in the production of reactive oxygen species (ROS) and a decrease in antioxidant activity (18).

HBOT consists of breathing 100% pure oxygen in a pressurized environment (hyperbaric chamber) to at least 1.4 atmospheres absolute (ATAs). The scientific basis for the use of oxygen at elevated pressures is based on the application of the Henry, Dalton and Boyle gas laws. There are other effects, the volumetric ones with an increase of 10 to 15 times the amount of oxygen in the plasma fraction, therefore, the diffusion distance from the vascular space to the tissues increases, and this is directly proportional to the pressure used (19, 20). The aim of this treatment is to evaluate the effect of HBOT on gene expression of superoxide dismutase 1 and 2 (SOD1 and SOD2), pro-inflammatory cytokines (TNF α , IL-1 β , IL-12, IL-4, as well as oxidative (NLRP3) and antioxidant (GPX2) enzymes in patients with diabetic foot.

Intermittent exposure to hyperbaric oxygen increases oxygen saturation by 100% in the blood (21, 22) and stimulates various biological processes that promote healing in numerous clinical conditions in which hypoxia is the dominant element (23-25). Hyperbaric oxygen therapy stimulates plasma antioxidant responses and regulates angiogenesis and vascular tone processes by increasing vascular endothelial growth factor levels and decreasing endothelin-1 levels. Different factors including age, oxidative stress (OS), diabetes and chronic inflammation play an important factor in the development of diabetic foot (26-27). It is assumed that the hyperbaric chamber increases the levels of circulating free fatty acids, and chronic inflammation may be associated with an increase in the production of reactive oxygen species (ROS) and a decrease in antioxidant activity (28).

Justification:

Mexico is a country where there is a high population of patients with diabetic foot and little research in response to non-invasive treatments such as hyperbaric chamber. Therefore, studies are needed to determine the mechanisms by which complications are triggered in these patients and to determine possible molecular markers for their timely treatment.

Research question:

In Mexican patients diagnosed with diabetic foot, what are the gene expression changes in inflammation and oxidative stress in diabetic foot patients treated with hyperbaric oxygen?

Hypothesis:

Patients diagnosed with diabetic foot will have significant changes after hyperbaric treatment such as increased gene expression in the antioxidant response and decreased gene expression in the inflammatory response.

General Objective:

To evaluate gene expression changes in inflammation and oxidative stress in diabetic foot patients treated with hyperbaric oxygen.

Specific objectives:

□ To evaluate the clinical and biochemical characteristics of the included patients according to sex.

□ To evaluate the gene expression of SOD, CAT, GPX, GRd, NLRP3, IL-1b, Casp-1, IL-4, IL-6, IL-10 and IL-13 in the basal state, at 12 and 30 sessions of treatment in the hyperbaric chamber.

Methodology:

Type of study: quasi-experimental, longitudinal, prolective, analytical study.

Characteristics of the population:

Women and men older than 18 years, with Diabetes type 2, residents of the CDMX, with diabetic foot with hyperbaric treatment, attended at the hospital of specialties in diabetes, secretary of health, accepted and signed the informed consent form.

Selection criteria:

Men and women with diabetic foot and hyperbaric treatment. Ages 30-60 years. Signed informed consent form.

Exclusion:

Patients with diabetic foot without presence of dermatologic lesions.

Elimination:

Patients who decided to abandon the protocol. Incomplete data for any variable.

Sample size:

15 patients with diabetic foot.

Operationalization of variables:

Variable	Туре	Measuring unit
Age	Quantitative	Years
Sex	Qualitative	Male/ female
Systemic blood	Quantitative	Milimeters of mercury
pressure		
Waist	Quantitative	Centimeters
Dislipidemias	Qualitative	Positive or negative
Anaemia	Qualitative	Positive or negative
Tabaquism	Qualitative	Positive or negative
Charcot's foot	Qualitative	Positive or negative
Chronic kidney	Qualitative	Positive or negative
disease by CKD-		
EPI I-III		
Insuficiencia	Qualitative	Positive or negative
venosa periférica		
Glucosa en sangre	Quantitative	milligrams/ deciliters
Colesterol	Quantitative	milligrams/ deciliters
Triglicéridos	Quantitative	milligrams/ deciliters
Basal glycosylated	Quantitative	Percentage
hemoglobin basal		
Creatinina	Quantitative	milligrams/ deciliters
Tasa de filtrado	Quantitative	milliliters/ square meter of body surface area
glomerular		
glycosylated	Quantitative	Percentage

hemoglobin at 3		
months		
Wagner's	Qualitative	Wagner
classification for		Grade 0: Absence of ulcers in a high-risk foot.
diabetic feet		Grade 1: Superficial ulcer involving the full
		thickness of the skin but no underlying
		tissues.
		Grade 2: Deep ulcer, penetrating to ligaments
		and muscles but not involving bone or
		abscess formation.
		Grade 3: Deep ulcer with cellulitis or abscess
		formation, almost always with osteomyelitis.
		Grade 4: Localized gangrene.
		Grade 5: Extensive gangrene involving the
		entire foot.
Gene expression	Qualitative	International units
SOD, CAT, GPX,		
GRd, NLRP3, IL-		
1b, Casp-1, IL-4,		
IL-6, IL-10 e IL-13.		

Procedure:

- 1. Patients attended at the diabetic foot clinic in the CDMX were invited to participate. 2.
- 2. An informed consent process was carried out with the patient's signature to agree to participate in the study.
- 3. Questions were asked about their personal pathological and non-pathological history.
- 4. Three tubes of blood samples were taken for determination of blood biometry, urea, creatinine, cholesterol, triglycerides, glycosylated hemoglobin. A 4 ml tube

with EDTA was taken to measure the gene expression of SOD, CAT, GPX, GRd, NLRP3, NLRP3, IL-1b, Casp-1, IL-4, IL-6, IL-10 and IL-13.

- 5. Complementary DNA (cDNA) synthesis was carried out following the instructions of the Transcriptor First Strand cDNA Synthesis kit (Roche Diagnostics), using a mixture of random hexamer primers, nitrogenous bases (A, T, G and C), reaction buffer, RNase inhibitor and Reveso Transcriptase enzyme. The retrotranscription reaction was carried out in a thermocycler (Eppendorf Mastercycler) programmed at an initial temperature of 25°C for 15 minutes, 45°C for 60 minutes and 72°C for 15 minutes.
- 6. The gRT-PCR technique to determine relative expression, a "master mix" (10 μ L) was prepared in microtubes for the LightCycler nano (Roche Diagnostics), the mix was composed of 100 nM forward oligonucleotides, 100 nM reverse oligonucleotides, 100 nM hydrolysis probe (Human Universal Probe Library, Roche Diagnostics), 2 µL TagMan master (Tag-polymerase), 0. 5 U LightCycler Uracil-DNA glycosylase, and 2 µL of DNAc (500 ng). The mixture was subjected to different temperature changes in the LightCycler Nano Real-Time PCR System (Roche Diagnostics) under the following conditions: initial incubation (denaturation) at 95 °C for 10 minutes, followed by 45 cycles of: denaturation (95 °C for 10 seconds), allylation of oligos to cDNA (60 °C for 30 seconds), and extension (copying) of the cDNA strand (72 °C for 1 minute). The specific sequences used to design the oligonucleotides used in gRT-PCR were ProbeFinder: designed using the online software https://lifescience.roche.com/shop/en/us/overviews/brand/universal-probelibrary.
- Relative RNAm expression of genes was normalized to the relative expression levels of the housekeeping gene (18s). Relative quantification (normalization) of gene expression was determined using the 2-ΔΔΔCT method.

Statistical analysis

In the analysis, qualitative variables are presented in frequencies and percentages, compared with the Chi-square test; quantitative variables according to the Shapiro-Wilk normality test, normally distributed variables are presented in means and standard deviation, compared with Student's t-test, those related with ANOVA test; quantitative variables of free distribution are presented in medians and interquartile ranges, compared with Mann Whitney U-test, those related with Kruskall-Wallis test. Data analysis was carried out with SPSS version 23, Graph Pad Prisma. A value p<0.05 was taken as statistical significance, 95% confidence interval (95%CI).

Ethical aspects:

The project was carried out in accordance with the General Health Law on Health Research published in the Official Journal of the Federation on February 7, 1984, published in the Official Journal of the Federation the General Health Law, regulating the third paragraph of Article 4 of the Political Constitution of the United Mexican States, which came into force on July 1 of the same year; as well as the guidelines of the Declaration of Helsinki of the World Medical Association. of the Political Constitution of the United Mexican States, which came into force on July 1st of the same year; as well as the guidelines of the Declaration of Helsinki of the World Medical Association on Ethical Principles for Medical Research Involving Human Subjects according to the 64th General Assembly, Fortaleza, Brazil, October 2013. The study is of greater than minimal risk, adhering to Chapter 1, Article 17, Section III of the ethical aspects of research on human beings, the authorization of the participants will be requested through an Informed Consent Letter (ICF) where the objective of the study and its significance, the procedures, the potential benefits and the possible risks will be stated; the name of those responsible for the study will also be mentioned and the autonomy and freedom they have to participate will be clarified.

In addition, according to the Helsinki declaration, specifically paragraph 33 of the last amendment of 2013, we will mention to the patient the possible benefits, risks, costs and efficacy of any new intervention, being evaluated by comparison with the best proven interventions, in this study the patient will be told which intervention could be more effective. As part of the ethical considerations, it will be informed that 14 ml of blood (one tablespoonful) will be drawn and that this amount does not put the health of the participants at risk, producing minimal discomfort with the aim of studying the presence of biochemical alterations.

Biosafety aspects.

- The present study has safety implications when obtaining blood samples, which can be considered infectious-contagious material. In the present study, the authors and co-authors are aware of and adhere to the General Law of Ecological Equilibrium and Environmental Protection and the General Law for the Prevention and Integral Management of Waste, which are of public order and social interest, Official Mexican Standard NOM-CRP-001-ECOL/1993, which establishes the characteristics of hazardous waste, the list of such waste and the limits that make a waste hazardous due to its toxicity to the environment; Official Mexican Standard NOM-002-SCT/2003 List of the most commonly transported Hazardous Substances and Materials; Official Mexican Standard NOM-002-SCT/2003 List of the most commonly transported Hazardous Substances and Materials; Official Mexican Standard NOM-002-SCT/2003 List of the most commonly transported Hazardous Substances and Materials; Official Mexican Standard NOM-002-SCT/2003 List of the most commonly transported Hazardous Substances and Materials; Official Mexican Standard NOM-002-SCT/2003 List of the most commonly transported Hazardous Substances and Materials; Official Mexican Standard NOM-002-SCT/2003 List of the most commonly transported Hazardous Substances and Materials; Official Mexican Standard NOM-002-SCT/2003 List of the most commonly transported Hazardous Substances and Materials; Official Mexican Standard NOM-002-SCT/2003 List of the most commonly transported Hazardous Substances and Materials; Official Mexican Standard NOM-002-SCT/2003 List of the most commonly transported Hazardous Substances and Materials; Official Mexican Standard NOM-002-SCT/2003 List of the most commonly transported Hazardous Substances and Materials.

As the information will be obtained through consultation with highly trained personnel with more than 10 years of experience, without endangering the health or physical integrity of health personnel or patients, the environment will not be affected since we have the training for the handling of RPBI, with full respect for the rights of patients avoiding any unnecessary physical or mental suffering or damage as dictated by the Nuremberg Code 1947.

Bibliographic references

1. Loyola-Leyva A., et al., (2019). Altered erythrocyte morphology in Mexican adults with prediabetes and type 2 diabetes mellitus evaluated by scanning electron microscope. Microscopy, pp: 1-10. doi: 10.1093/jmicro/dfz011.

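### A directional hypothesis is tested on 11 genes at p<0.05 with no main contrast, no complete gene-to-class assignment, no rule for support and no multiplicity control

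*Combined protocol and SAP*

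**What the plan says.** All references are to the combined protocol and SAP.

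- **Hypothesis.** Significant changes are expected after treatment, described as "increased gene expression in the antioxidant response and decreased gene expression in the inflammatory response". Direction is stated for two classes of response; no gene is named.
- **Specific objectives.** One undivided list: "gene expression of SOD, CAT, GPX, GRd, NLRP3, IL-1b, Casp-1, IL-4, IL-6, IL-10 and IL-13 in the basal state, at 12 and 30 sessions". That is 11 names at three time points, with no primary gene or time point.
- **Introduction, aim sentence.** This is the only place that labels genes by class, and its gene list differs from that of the objectives. It calls IL-1β and IL-4 pro-inflammatory (with TNF-α and IL-12, which are not in the objectives), and continues "as well as oxidative (NLRP3) and antioxidant (GPX2) enzymes in patients with diabetic foot".
- **Sample size.** "15 patients with diabetic foot", without power, effect size or SD.
- **Statistical analysis.** Tests are chosen by variable type and normality. Related normal variables go to an ANOVA; for the non-normal ones the text reads "compared with Mann Whitney U-test, those related with Kruskall-Wallis test". The only decision rule is "A value p<0.05 was taken as statistical significance, 95% confidence interval (95%CI".
- **Operationalization of variables.** Gene expression is typed as qualitative.
- **Elimination.** Patients are removed for "Incomplete data for any variable".

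**The concern.** A reader cannot tell from the plan which result would support the hypothesis. It could be one gene or several, one class or both, session 12 or session 30. Eight of the 11 genes carry no label that matches either class: NLRP3 is called oxidative, which is neither class, and SOD, CAT, GRd, Casp-1, IL-6, IL-10 and IL-13 have none. For those eight, a rise or a fall could be presented afterwards as the expected response.

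At stake is the meaning of a positive finding. With 11 genes and an unadjusted 0.05, some readings of the plan produce apparent support by chance far more often than 1 in 20, and others far less often. Because the plan does not choose between them, the choice could be made once the expression results are known.

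**Working it through.** **Inputs from the documents:** 11 genes, three time points, threshold 0.05, n=15.

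**Assumptions:** no true effect; two-sided tests, since sidedness is not stated; each gene tested separately, which is inferred because the statistical analysis section does not mention genes; expression analysed as a quantitative variable despite its qualitative label; between-gene correlation 0 / 0.3 / 0.6, since the documents give none. Where directions are fixed, I assume 4 genes up and 7 down; splits of 5/6 and 6/5 change the results by no more than 0.01. Figures for correlated genes are simulated.

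The sample size of 15 cannot be reproduced, because no effect size, SD or power is given.

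**Exact results for independent genes**

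- One gene in its predicted direction is enough (0.025 per gene): 1 − 0.975^11 = 0.243.
- Any change in any gene is enough: 1 − 0.95^11 = 0.431.
- Direction fixed only for the three labelled genes: 1 − 0.975^3 × 0.95^8 = 0.385.
- At least one antioxidant gene up and one inflammatory gene down: (1 − 0.975^4) × (1 − 0.975^7) = 0.0963 × 0.1624 = 0.016.
- Predicted direction after adjustment: Holm's first step uses 0.05/11, so 0.05/22 in one direction. 1 − (1 − 0.05/22)^11 = 0.025, ignoring the small addition from later Holm steps.

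**Chance of apparent support under each reading**

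| Reading | correlation 0 | 0.3 | 0.6 |
|---|---|---|---|
| One gene, predicted direction, baseline to session 30, all directions fixed | 24% | 22% | 18% |
| The same, Holm over 11 genes | 2-3% | 2-3% | 2-3% |
| Any change in any gene, repeated-measures ANOVA | 43% | 39% | 28% |
| Any change in any gene, ordinary one-way ANOVA, within-patient correlation 0.3 | 17% | 15% | 11% |
| The same, within-patient correlation 0.5 | 5% | 5% | 4% |
| At least one gene up in one class and one down in the other | 1.6% | 0.3% | <0.1% |

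The first two rows are the matched before-and-after comparison, since both count only predicted-direction results at session 30.

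Kruskal-Wallis on the related samples behaves like ordinary ANOVA. Its error per gene is 0.0177 and 0.0053 at within-patient correlation 0.3 and 0.5, so over 11 independent genes it is 1 − (1 − 0.0177)^11 = 0.178 and 1 − (1 − 0.0053)^11 = 0.057. The cost there is power: for a change of 0.78 SD at session 30, with half of it at session 12, power is 53% and 34%, against 73% for repeated-measures ANOVA.

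**Power cost of adjusting** (paired t-test, noncentral t, 80% power, in SDs of the within-patient change)

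- n=15: 0.78 at 0.05; 1.11 at 0.05/11.
- n=12, assumed, if the elimination rule removes three patients: 0.89 and 1.30.
- For a true change of 0.78 SD at n=15, power per gene falls from 80% to 40% at 0.05/11. If all 11 genes shift by that much, it is about 51-53% with Holm, and about 76% with false-discovery-rate control for independent genes.

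**The case against.** Four arguments on the other side have weight.

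1. **The hypothesis joins its two classes with an and.** Read as requiring both, chance support is 1.6% or less. That is a fair reading, but the sentence offers the two changes as examples of what is expected, and no rule requires both. A single significant gene could still be reported as support.

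2. **The 43% figure is not clearly the plan's own.** The text says only ANOVA for related variables. Repeated-measures ANOVA is an interpretation, and an ordinary ANOVA or Kruskal-Wallis on the same data can bring the chance near 5%. This stands. On that route the main loss is power. A reader might also infer a still higher figure from testing all pairwise time contrasts, but the statistical analysis section names no such procedure.

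3. **Direction and labels are not wholly absent.** Direction is given by class, and the aim sentence labels GPX2, IL-1β and IL-4 in a way that matches a class. The IL-4 label rests on a bracket that is not closed in the available text. What is missing is a complete assignment for the 11 genes.

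4. **This is a small mechanistic study.** The research question is open and the objectives speak of evaluating. An exploratory label would be enough, but the plan does not use one: it predicts significant changes and sets a significance threshold.

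**Conclusion.** The gap is real and worth repairing. The plan has a directional hypothesis, 11 genes, three time points and one unadjusted threshold. It has no main contrast, no complete assignment of genes to classes, no rule for support and no multiplicity control.

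A reader might infer that the plan has a 43% false-positive rate, or that it states no directions at all. The documents support neither. The size depends on the reading, from under 0.1% to 43% at n=15. On matched terms, one gene in its predicted direction counts by chance in about 24% / 22% / 18% of studies, against about 2-3% after Holm.

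Confidence is high for the omissions and lower for any single percentage. The percentages rest on assumed correlations, an assumed 4/7 split, two-sided tests and separate quantitative analysis of each gene.

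**What to change.** 1. Assign each of the 11 genes to antioxidant, inflammatory or neither, with an expected direction. Name baseline to session 30 as the main contrast and session 12 as secondary. State that full support needs both classes to change in the predicted direction.
2. Use within-patient tests on log2 expression normalised to 18s. Report estimates with 95% CIs, and p values adjusted over the 11 genes by Holm or false discovery rate. Correct the qualitative label for gene expression.
3. The procedure is written in the past tense. If expression results have already been seen, or if no adjustment is made, label all single-gene results exploratory and do not claim that the hypothesis is confirmed.
4. Optional: one direction-signed score per class (per patient, the mean signed log2 change over that class's genes, each scaled by its baseline SD), with Holm across the two scores. If data have been seen, label the scores post hoc.

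Cost: no new patients, samples or assays. Adjustment costs the power shown in the working, less with false discovery rate if many genes shift. A score dilutes a single-gene effect: if one of four genes shifts by 1.0 SD at an assumed correlation of 0.4, the score shows only 0.25/√((1 + 3 × 0.4)/4) = 0.34 SD.

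### The elimination rule deletes whole patients for any missing variable, so usable expression samples are discarded and expression change is estimated only in complete cases

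*Combined protocol and SAP*

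**What the plan says.** The general objective is "To evaluate gene expression changes in inflammation and oxidative stress in diabetic foot patients treated with hyperbaric oxygen". The first specific objective is "To evaluate the clinical and biochemical characteristics of the included patients according to sex". The second asks for expression of 11 genes "in the basal state, at 12 and 30 sessions of treatment in the hyperbaric chamber".

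The Elimination entry, listed separately from Exclusion, reads "Patients who decided to abandon the protocol. Incomplete data for any variable". It does not limit which variables count. The table under Operationalization of variables, which follows shortly after, has 18 rows besides gene expression. Among them are waist, lipids, smoking, Wagner grade and a follow-up HbA1c ("hemoglobin at 3" months).

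The sample size is given only as "15 patients with diabetic foot", with no derivation and no statement of whether this is the number enrolled or analysed. Procedure step 4 describes a single tube for the genes ("with EDTA was taken to measure the gene expression of SOD, CAT, GPX, GRd").

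The Statistical analysis section begins "In the analysis, qualitative variables are presented in frequencies and percentages, compared with the Chi-square test" and goes on to name summaries and tests for quantitative variables, including ANOVA for related normal ones. It defines no analysis set, no handling of missing values and no sensitivity analysis.

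**The concern.** The rule ties a patient's place in the expression analysis to data that the expression comparison does not use. Two kinds of patient show the problem:

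- A patient with all three expression samples but no 3-month HbA1c is removed entirely.
- A patient who leaves after session 12 may have both samples for the basal-to-session-12 comparison, yet is also removed.

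The objective concerns treated patients, but the estimate would describe only those with complete records. The description by sex under the first specific objective would be narrowed in the same way.

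No control arm is described, so the result is a before-after change and depends directly on who remains in the set. With about 15 patients, losing even one or two for reasons unrelated to expression is a cost that can be avoided.

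**Working it through.** **What the plan's own figure allows.** The 15 cannot be reproduced: no effect size, standard deviation, power or dropout rate is given. Everything below is illustration under stated assumptions.

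**Inputs.**
- From the documents: 15 patients; expression at basal, session 12 and session 30; one further later item, HbA1c at 3 months. That makes four collection events. Loss is counted by event because the genes share one tube, so gaps cluster.
- Assumed: 15 is the number enrolled; loss per event q = 1%, 5% or 10%, independent across events; two-sided 5% level and 80% power.

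**Patients left, 15 × (1−q)^k.**

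| Set | k | q = 1% | q = 5% | q = 10% |
|---|---|---|---|---|
| Written rule: all four events | 4 | 14.41 | 12.22 | 9.84 |
| All three expression samples | 3 | 14.55 | 12.86 | 10.94 |
| The two samples of one pairwise comparison | 2 | 14.70 | 13.54 | 12.15 |

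**Cost of the rule.**
- Against complete triplets: 15 × [(1−q)^3 − (1−q)^4] = 0.15, 0.64, 1.09 patients.
- Against a pairwise available-case comparison: 15 × [(1−q)^2 − (1−q)^4] = 0.29, 1.32, 2.31 patients.

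**If leaving is permanent (monotone loss) instead of independent.**
- Basal to session 30: the cost is 0.15, 0.64 or 1.09 if month 3 falls after session 30, and zero if it falls earlier. The documents do not say which.
- Basal to session 12: the cost is 0.29, 1.32 or 2.31 if month 3 falls after session 12.

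The abandonment half of the rule therefore acts mainly on the session-12 comparison. A patient who leaves before session 30 has no session-30 sample under either rule.

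**Detectable standardised paired change.** Solve P(|T| > t(0.975, n−1)) = 0.80 for d, where T is noncentral t with n−1 degrees of freedom and noncentrality d√n:

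| n | 15 | 12 | 11 | 10 |
|---|---|---|---|---|
| d | 0.78 | 0.89 | 0.94 | 1.00 |

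At q = 10%, with counts rounded to whole patients, the rule moves the detectable change from about 0.94 (n = 11) to 1.00 (n = 10) relative to complete triplets. Relative to pairwise available cases it moves from 0.89 (n = 12) to 1.00. This paired calculation is a common yardstick, not the power of the three-time-point test itself.

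**What the model leaves out.** It treats basal clinical data as collected together with the basal sample. An isolated gap, such as a missing waist, would cost one further whole patient each time.

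**The case against.** The strongest case on the other side concerns size and remedy, not the text of the rule.

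- *The plan may need complete expression data anyway.* The Statistical analysis section names ANOVA for related variables and no pairwise comparison. A classical repeated-measures ANOVA uses only complete triplets whatever the elimination rule says. This stands: the smaller cost (0.15, 0.64 or 1.09 patients) is the fair comparison with that analysis, and the larger one depends on a comparison that the plan does not name. But the form of ANOVA is not specified, and the named rank test would not need complete triplets. Nor would either test justify removing a patient for a missing waist or HbA1c value.
- *The effect may be nil.* This also stands. No missingness is reported. If 15 is the number analysed, no power is lost relative to that number, although selection could remain.
- *Changing the main analysis after the fact is itself a risk.* The past tense in the Procedure and Statistical analysis sections suggests that data collection is finished. This stands and shapes the fix.

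A reader might also infer that the rule would devastate the sample. Treating all 51 values per patient (18 + 11 × 3) as independently missing at 0.5%, 1% or 2% would leave 11.6, 9.0 or 5.4 of 15 patients. The documents do not support that: the genes come from one tube, so their gaps would occur together, and no rate is given.

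**Conclusion.** The point holds as a cheap improvement. As written, the rule is patient-level deletion for any missing listed variable or for leaving, and nothing in the Statistical analysis section offsets it. Usable expression samples are discarded, and the expression result describes complete cases only.

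The illustrated cost is modest: about one patient at 10% loss per event against complete triplets, and a little over two against pairwise available cases. These figures rest on 15 enrolled, four collection events, independent loss and assumed rates.

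A reader might infer that the rule biases the estimated change, or flatters the treatment. The documents do not support that. Bias due to the rule arises only if the extra missingness (for example in 3-month HbA1c) is related to expression change, and nothing in the documents shows this. Its size and direction cannot be determined, so no bias figure is offered. Nor do the documents show that any patient was actually eliminated.

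**What to change.** - Remove a patient from an expression comparison only if the expression samples that it needs are missing, or if consent for use of the data is withdrawn.
- Let a missing clinical variable remove the patient only from that variable's summary.
- If outcome data have already been seen, report the analysis under the written rule together with an available-case analysis labelled as such. If not, make the available-case analysis the main one and the complete-case analysis the sensitivity analysis.
- Report how many patients were eliminated, when (before session 12, between sessions 12 and 30, or later) and why. State whether 15 is the number enrolled or analysed.

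The cost is small: a wording change or a short additional analysis, and patient numbers that vary by comparison. The change does not remove bias from expression samples that are themselves missing.

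### Wagner grade is an ordered severity scale but is typed Qualitative, so the by-sex comparison falls to an unordered Chi-square test (minor; descriptive objective only)

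*Combined protocol and SAP*

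**What the plan says.** In the table under Operationalization of variables, the row for Wagner's classification reads "Wagner's Qualitative Wagner", so its declared type is Qualitative. The same row lists the levels in rising severity, from "Grade 0: Absence of ulcers in a high-risk foot" up to "Grade 5: Extensive gangrene involving the" entire foot.

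The Statistical analysis section chooses tests by type. For one type, "qualitative variables are presented in frequencies and percentages, compared with the Chi-square test". For another, "quantitative variables of free distribution are presented in medians and interquartile ranges, compared with Mann Whitney U-test". It names no ordinal or trend test. The threshold is given as "A value p<0.05 was taken as statistical significance", without saying whether tests are two-sided.

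The first of the specific objectives is "To evaluate the clinical and biochemical characteristics of the included patients according to sex". The sample size is "15 patients with diabetic foot". The documents do not name a Wagner-by-sex test. It follows from that objective, the listing of Wagner grade among the study variables, and the general rule for qualitative variables.

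**The concern.** Pearson's Chi-square on a 2 × K table treats the K grades as unordered labels. A consistent tendency for one sex to have worse feet is therefore tested no more sharply than an arbitrary scatter of the same size. Replacing it with an exact version of the same unordered test would deal with the small expected counts but would still ignore the order, so the two faults are distinct.

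Wagner grade is the only graded measure of foot severity in the table; Charcot's foot is recorded only as positive or negative. At stake is whether a real severity gradient between men and women is reported as no difference in the description of the patients.

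**Working it through.** The documents give no power, effect size or sample-size derivation for this comparison, so there is no figure of the plan's own to reproduce.

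**Inputs from the documents:** N = 15; alpha 0.05; six ordered grades; Chi-square for qualitative variables.

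**Assumed, because not stated:** two-sided testing; sex splits 8:7, 10:5 and 12:3; the grade distribution; a proportional-odds shift with odds ratio (OR) 4 to 20. The Exclusion criterion removes patients without skin lesions, which may leave Grade 0 empty, so the main illustration uses three to five occupied grades.

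**1. Order is unused: a constructed example.** Take eight patients of one sex with grades 2,2,3,3,3,3,4,4 and seven of the other with 1,1,1,2,2,2,3. Counts for grades 1 to 4 are 0,2,4,2 and 3,3,1,0, with totals 3,5,5,2.

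- Expected counts (row total × column total / 15) are 1.60, 2.67, 2.67, 1.07 and 1.40, 2.33, 2.33, 0.93.
- X² = Σ(O − E)²/E = (1.600 + 0.167 + 0.667 + 0.817) + (1.829 + 0.190 + 0.762 + 0.933) = 6.96 on 3 df, p = 0.073.
- The exact version of this unordered test gives p = 0.091.
- Midranks for grades 1 to 4 are 2, 6, 11 and 14.5. The first group's rank sum is 2×6 + 4×11 + 2×14.5 = 85, so U = 85 − 8×9/2 = 49 against a null mean of 8×7/2 = 28. Exact p over all 6,435 allocations is 0.013.

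Now swap the labels of grades 1 and 3. X² stays at 6.96, because the columns have only been reordered. The midranks become 3, 8, 12 and 14.5, the rank sum is 4×3 + 2×8 + 0×12 + 2×14.5 = 57, and U = 57 − 36 = 21, now close to 28. Only the rank test responds to the order.

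**2. Size of the loss: illustration only.** Power by simulation under a monotone shift (1,500 to 20,000 tables per setting, depending on the run). A dash means that test was not run in that setting.

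| Occupied grades | Split | OR | Chi-square | Exact unordered | Exact Mann-Whitney | Gain over Chi-square | Gain over exact unordered |
|---|---|---|---|---|---|---|---|
| 3 | 8:7 | 4 | 0.21 | 0.18 | 0.22 | 0.01 | 0.05 |
| 3 | 8:7 | 10 | 0.49 | 0.44 | 0.53 | 0.04 | 0.08 |
| 3 | 12:3 | 4 | 0.14 | 0.11 | 0.14 | 0.00 | 0.03 |
| 4 (20/35/30/15%) | 8:7 | 10 | 0.35 | 0.36 | 0.56 | 0.21 | 0.20 |
| 4 (20/35/30/15%) | 8:7 | 20 | 0.60 | 0.61 | 0.80 | 0.20 | 0.19 |
| 4 | 12:3 | 4 | 0.11 | – | 0.15 | 0.04 | – |
| 4 | 12:3 | 10 | 0.28 | – | 0.37 | 0.09 | – |
| 5 (equal) | 8:7 | 10 | 0.33 | 0.39 | 0.60 | 0.27 | 0.21 |

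Gains in the three-grade rows are taken before rounding. With five grades, a 10:5 split and OR 10, the gain over Chi-square is 0.26. It does not differ from the 0.27 in the last row beyond simulation error: the standard error of that difference with 3,000 tables is at most about √(0.33×0.67/3000 + 0.60×0.40/3000) = 0.012. With only two occupied grades the two asymptotic tests coincide and there is no gain.

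**3. What the gap contains.** In the five-grade row, 0.39 − 0.33 = 0.06 of the 0.27 disappears once the unordered test is made exact. That part reflects the sparse table. The remaining 0.21 is due to ignoring the order.

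**4. The reverse case.** For a non-monotone difference simulated at 8:7, Chi-square has power 0.46 and Mann-Whitney 0.07.

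**The case against.** The strongest reply is that this matters little. The research question, hypothesis and general objective concern within-patient changes in expression at baseline, 12 and 30 sessions, and no hypothesis concerns sex. The plan already promises frequencies, so a reader can see any shift among 15 patients without a p-value. At OR 4, with three to five occupied grades, exact Mann-Whitney itself has power of only about 0.14 to 0.27, so the change does not make the comparison informative for modest shifts. The rank test is also worse when the difference is not monotone. All of this stands, and it sets the weight of the point. None of it shows that an unordered test suits an ordered scale.

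Two stronger readings are tempting, and the documents support neither.

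- A reader might infer that the plan forfeits a definite amount of power, say 0.16 to 0.27. Such a range needs a sex split, a grade distribution and an effect size that are not given. It comes from an 8:7 split, four or five occupied grades and odds ratios of 6 to 20, and its upper end includes the sparse-table effect.
- A reader might infer that a severity imbalance between the sexes would distort the expression results. This is a single-group before-after study. Men and women are not the treatment groups being compared, and such an imbalance does not bias a within-patient change.

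**Conclusion.** The mis-typing is established from the text: an ordered scale is declared Qualitative, and the only rule for that type is an unordered test. That this test would be applied to Wagner grade by sex is an inference, though the natural one.

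The size of the loss is an illustration. For a monotone shift in 15 patients, with assumed splits from 8:7 to 12:3, three to five occupied grades and OR 4 to 20, exact Mann-Whitney gains from about 0 (three grades) to about 0.26 (four or five grades) over Chi-square, and about 0.02 to 0.22 over the exact unordered test. Fewer occupied grades, a more uneven split or a smaller shift all tend to bring it down. The point is a minor improvement to a descriptive secondary objective and leaves the gene-expression conclusions untouched.

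**What to change.** In the variables table, change the type of Wagner's classification from Qualitative to ordinal. In the Statistical analysis section, add: Wagner grade is presented as the frequency per grade with median and interquartile range, and compared by sex with the exact two-sided Mann-Whitney U test, with midranks for ties. Keep Chi-square, or an exact version of it, for the unordered yes/no variables.

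The cost is one table cell and one sentence, using a test the plan already names. The trade-off is lower sensitivity to a non-monotone difference, which the retained frequency table would still show. The procedures are written in the past tense, so if the by-sex table has already been examined, report the change as made afterwards and give both p-values.
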